## 1. OBJECTIVES

### 1.1 Primary Objective(s)

To establish the objective response rate, using RECIST criteria, to the combination Treatment of Interferon alpha-2b and 5-FU/Capecitabine in patients with unresectable and/or metastatic cutaneous squamous cell carcinoma of the skin

### 1.2 Secondary Objective(s)

To establish the progression free and overall survival at one year, adverse events, and safety profile of the combination treatment of Interferon alpha-2b and 5-FU/Capecitabine in patients with unresectable and/or metastatic cutaneous squamous cell carcinoma of the skin

## 2. BACKGROUND

### 2.1 Study Disease

While squamous cell carcinoma of the skin is a very common cancer, the true number of cutaneous squamous cell carcinoma (CSCC) cases are difficult to determine, as the national SEER database does not capture non-melanomatous skin cancers (NMSC). However, it has been estimated that there are over 1.5 million cases of NMSC (75% Basal cell carcinoma and 25% Squamous cell carcinoma) diagnosed annually in the US. Besides the known risk factor of UV exposure, an increase in cutaneous squamous cell carcinoma (CSCC) has been noted as a result of rising rates of transplants (BMT and solid organ) and the widespread use of immunosuppressive agents.

The majority of CSCCs are local in origin and are therefore treated with focal therapies including surgery, cryotherapy, topical chemotherapy (imiquimod, topical 5-FU), photodynamic therapy, and radiation therapy. Local control with these therapies typically exceeds 90% and even in patients with recurrent local disease, local control rates remain quite high.

Seventy-five percent of recurrences occur in the first two years and typically recur locally or in regional lymph nodes placing patients at high risk for developing distant metastasis. While metastatic squamous cell cancer of the skin is rare, its' consequences are profound. In one study, 34 of 695 cases of cutaneous squamous cell carcinoma developed metastases for a metastatic rate of approximately 5%. The overall mortality of all patients was 3.4%; however, the mortality rate in the metastatic group exceeded 70%. Similarly, in CSCC patients with distant metastasis, Alam et al. described a 5-yr survival rate of less than 10%.

Thus, while many patients are cured with local therapy, those with unresectable locoregional disease or known sites of distant metastasis have an increased mortality rate. Presently there is no standard accepted treatment for unresectable or metastatic disease.

### 2.2 PEG Interferon alpha-2b

PEG Interferon (IFN) alpha-2b was approved in 2001 by the FDA for the adjuvant treatment of melanoma for those patients with residual microscopic or gross disease. Currently, IFN alpha-2b is also approved for use in patients with hepatitis C and used frequently in patients with renal cell carcinoma. The non-PEG formulation has been tested in a variety of tumor types including cutaneous squamous cell carcinoma.

The pegylated formulation of IFN alpha-2b was designed to protect IFN from proteolytic breakdown and extend the half-life of the protein. IFN alpha-2b is a protein produced by recombinant DNA techniques from a strain of *E. Coli* bearing a engineered plasmid containing

the interferon gene from human leukocytes. The drug comes in a lyophilized powder in a single-use vial and reconstituted with 0.7 mL sterile water. Peg-IFN alpha-2b is given SQ on a weekly basis from doses of 3 mcg/kg (maintenance) to 6 mcg/kg (induction therapy) in the setting of melanoma and doses of 1-1.5 mcg/kg in hepatitis C patients. Treatment periods range from 24-48 weeks for hepatitis C and 1-5 years for melanoma. Of note, IFN alpha-2a and -2b are related protein products, but PEG IFN alpha-2b was selected as it is dosed by body weight, has a more rapid absorption, and a wider distribution within the body.

The mechanism(s) of action had not been fully identified; however, it is considered an immunomodulatory cytokine that enhances the phagocytic and cytotoxic activity of macrophages and leukocytes.

The drug has a half-life of approximately 40 hours with a peak plasma time of 15-44 hours. It is excreted renally and dose reductions of 25-50% are recommended for moderate to severe renal impairment (Cr Cl <50 or <29 ml/min respectively). The drug is contraindicated for patients with a known hypersensitivity to IFN, patients with autoimmune hepatitis, or hepatic decompensation.

Common adverse events include: headache, fatigue, injection site reactions, depression, emotional lability, suicidal ideation, insomnia, alopecia, fever, transaminitis, anorexia, GI irritation (abdominal pain, nausea, diarrhea), arthralgias, myalgias, chills, and rash. Severe adverse reactions include: neuropsychiatric reactions, arrhythmia, cardiovascular decompensation, retinopathy resulting in blindness, hepatic failure, and can result in new or worsening of endocrinopathies.

Currently there are no known drug interactions, however, data suggest possible impairment of CYP2C9 (increased activity) and CYP2D6 (decreased activity). When combined with drugs with narrow therapeutic windows, it is recommended to monitor those drug levels frequently.

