#### **4.3 Interferon Administration**

Drug administration will occur on an outpatient basis at the infusion center at Moffitt Cancer Center. Dose will be weight-based. Starting treatment doses of 3 mcg/kg will be given SC injection in the thigh, abdominal wall, or upper arm every week for a total of 27 weeks as tolerated. Patients will be premedicated with 650 mg of acetaminophen or 400 mg of ibuprofen as tolerated. For severe side effects, dose reductions are allowed as discussed in Section 5. Reported adverse events and potential risks are described in Section 6.

4.3.1 Storage: Drug stored in pharmacy per manufacturer's instructions.

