### **5. DOSING DELAYS/DOSE MODIFICATIONS**

#### **5.1 5-FU/Capecitabine**

A dose reduction will be instituted upon any grade 3 or 4 toxicity that is attributable to 5-FU/capecitabine. For all grade 3 or 4 toxicities related to 5-FU/capecitabine, the study treatment will be withheld for up to 3 weeks until the toxicity has resolved to CTCAE grade 1 or better (or back to baseline), and then treatment may be restarted. Dose reduction/re-challenge for each toxicity criterion will be managed as discussed in the sections that follow. Patients will be withdrawn from the study if toxicity does not resolve to  $\leq$  CTCAE grade 1 (or to baseline) within 3 weeks.

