#### **Other toxicities**

If  $\geq$  grade 3 toxicities directly attributable to 5-FU/capecitabine other than those discussed above occur (except fatigue, alopecia, or nausea/emesis in the absence of anti-emetics), therapy will be discontinued until the toxicity is  $<$  grade 2. If there is no evidence of tumor

progression, therapy may resume with a dose reduction according to Table 1. If treatment is required to be held for  $\geq$  3 weeks, then study treatment will be discontinued.

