## **5.2 Interferon Alpha-2b**

A dose reduction will be instituted upon any grade 3 or 4 toxicity that is attributable to Interferon alpha-2b. For all grade 3 or 4 toxicities related to IFN, the study treatment will be withheld for up to 3 weeks until the toxicity has resolved to CTCAE grade 1 or better, and then treatment may be restarted. Dose reduction/re-challenge for each toxicity criterion will be managed as discussed in the sections that follow. Patients will be withdrawn from the study if toxicity does not resolve to  $\leq$  CTCAE grade 1 within 3 weeks.

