**6.2 Expected potential toxicities of IFN alpha-2b:**

General: "Influenza-like" symptoms (mainly fever, headache, chills, myalgia, and fatigue)

Gastrointestinal: anorexia, nausea, diarrhea, vomiting, altered taste, abdominal pain, constipation, gingivitis, loose stools, dyspepsia

Hepatic: elevated SGOT, right upper quadrant pain

Psychiatric: depression, anxiety, nervousness

Dermatologic: alopecia, rash, pruritus, dry skin, dermatitis, hair discoloration

Respiratory: dyspnea, coughing, pharyngitis, sinusitis, nonproductive cough, nasal congestion, and bronchitis

Nervous system: headache, somnolence, dizziness, irritability, paresthesia, impaired concentration, amnesia, confusion, insomnia, hypoesthesia, vertigo, and decreased libido

Musculoskeletal: myalgia, musculoskeletal pain, and arthralgia  
Immunologic: nonspecific infection, viral infection, and herpes simplex  
Hematologic: neutropenia, anemia, thrombocytopenia, bleeding, and purpura  
Genitourinary: Amenorrhea, polyuria  
Cardiovascular: hypertension. Angina, arrhythmia, atrial fibrillation, bradycardia, cardiac failure, cardiomegaly, cardiomyopathy, coronary artery disorder, extrasystoles, heart valve disorder, hematoma, hypotension, palpitations, phlebitis, postural hypotension, pulmonary embolism, Raynaud's disease, tachycardia, thrombosis, and varicose vein have been reported in less than 5% of patients.  
Endocrine: aggravation of diabetes mellitus, goiter, hyperthyroidism, and hypothyroidism in less than 5% of patients.  
Metabolic: Hypertriglyceridemia, dehydration, hypercalcemia, hyperglycemia, and  
Ocular: Ocular side effects have included abnormal vision, blurred vision, diplopia, dry eyes, eye pain, lacrimal gland disorder, lacrimation, nystagmus, and photophobia in less than 5% of patients.  
Renal: increased BUN and renal insufficiency in less than 5% of patients.  
Hypersensitivity: Hypersensitivity side effects have included allergic reaction  
Local: injection site inflammation

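### Section 2.2 recommends interferon cuts at creatinine clearance below 50 and 29 mL/min, but the dosing rules do not apply them to a lower-grade or unattributed fall during treatment

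*Combined protocol and SAP*

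**What the plan says.** **Background.** Section 2.2 states that the drug is excreted renally and that "dose reductions of 25-50% are recommended for moderate to severe renal impairment (Cr Cl <50 or <29 ml/min respectively". It does not say which dose the percentages refer to. Earlier in the same section it lists "3 mcg/kg (maintenance) to 6 mcg/kg (induction therapy) in the setting of melanoma and doses of 1-1.5 mcg/kg in hepatitis C patients".

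**Entry.** Section 3.1.7 requires a clearance of at least 50 mL/min, by Cockcroft-Gault or 24-hour urine. Section 3.2.8 admits renal-transplant patients who agree to reduce immunosuppression and accept the risk of rejection and a return to dialysis.

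**Dosing.** Section 4.3: "Starting treatment doses of 3 mcg/kg will be given SC injection", weekly for 27 weeks, subject to tolerance. On reductions it says: "For severe side effects, dose reductions are allowed as discussed in Section 5".

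**Modification rules.** Section 5.2: "A dose reduction will be instituted upon any grade 3 or 4 toxicity that is attributable to Interferon alpha-2b". Its named items are fatigue, arthralgia/myalgia, weight loss, depression and GI toxicity. Section 5.1 has the matching rule for the other drug: "A dose reduction will be instituted upon any grade 3 or 4 toxicity that is attributable to 5-FU/capecitabine". Its residual clause concerns "toxicities directly attributable to 5-FU/capecitabine other than those discussed above occur" and steps down Table 1, the 5-FU/capecitabine dose table.

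**Expected toxicity.** Section 6.2 lists, for interferon, "increased BUN and renal insufficiency in less than 5% of patients".

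**Stopping and monitoring.** Sections 3.5 and 4.4 let the investigator remove a patient or end treatment. The Section 8 calendar shows weight and serum chemistry, including creatinine, at the start of cycles 1 to 3. It does not ask for clearance.

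**The concern.** The protocol states a dose recommendation and then leaves it out of the sections that control dosing. Nobody starts below the limit, so the question is what happens when clearance falls on treatment. The entry floor of 50 mL/min sits exactly at the first limit in 2.2, so a patient admitted near it has little or no margin. The protocol makes a fall foreseeable: renal insufficiency is an expected interferon toxicity, dehydration is listed for both drug groups in 6.1 and 6.2, and some transplant patients will be reducing immunosuppression.

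For capecitabine, Section 2.3 at least refers the reader to the package insert for renal dose changes. Section 2.2 has no such pointer, and no dosing section refers back to it. At stake is the safety of a few patients, who could go on receiving more of a renally cleared drug than the protocol itself recommends because no rule prompts the change.

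**Working it through.** The plan gives no figure to reproduce here. The check sets the rules side by side and then does the dose arithmetic.

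**1. Which rule applies when clearance falls below 50 mL/min on treatment?**

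| Event | Rule | Interferon dose reduction directed? |
|---|---|---|
| Grade 3-4, attributed to interferon | 5.2: hold up to 3 weeks, then reduce | Yes |
| Grade 3-4, attributed to 5-FU/capecitabine only | 5.1: study treatment held, then Table 1 | No; only 5-FU/capecitabine is reduced |
| Grade 3-4, attributed to neither (for example graft rejection) | 3.5 and 4.4 allow stopping | No |
| Below grade 3, any cause | Stopping at discretion; tolerance wording in 4.3 | No |

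The documents cite CTCAE version 4.0 but do not reproduce its renal cut-offs. Clearance below 29 may therefore already count as grade 3, which would put an interferon-attributed case in the first row. The second and third rows do not depend on that.

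**2. Recommended dose.** Reduced dose = base × 0.75 (below 50) or base × 0.50 (below 29). Excess of 3 mcg/kg = 3 / reduced dose − 1.

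| Base (mcg/kg) | Below 50 | Below 29 | 3 mcg/kg relative to these |
|---|---|---|---|
| 6 | 4.5 | 3.0 | no excess at either limit |
| 3 (trial start) | 2.25 | 1.5 | 33% and 100% above |
| 1.5 | 1.125 | 0.75 | 167% and 300% above |
| 1 | 0.75 | 0.5 | 300% and 500% above |

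Base 3 is the natural reading for this trial, but it is an assumption.

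**3. How large a fall is needed?** At constant age and weight, Cockcroft-Gault clearance is inversely proportional to creatinine. The creatinine ratio needed is therefore entry clearance / 50, or entry clearance / 29.

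| Entry clearance (mL/min) | To reach 50 | To reach 29 |
|---|---|---|
| 50 | any rise | 1.72× |
| 55 | 1.10× | 1.90× |
| 60 | 1.20× | 2.07× |
| 80 | 1.60× | 2.76× |
| 100 | 2.00× | 3.45× |

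A small rise matters only near the entry floor.

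**4. How many patients?** The documents do not say. The under-5% figure in 6.2 describes renal insufficiency with interferon, which is not the same event as clearance below 50. As an illustration only, an assumed 1% to 5% per patient gives 30 × 0.01 = 0.3 to 30 × 0.05 = 1.5 of 30 enrolled patients. No transplant count is given.

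**5. Do the existing dose levels fit?** Table 2 level −1 is 2 mcg/kg, a cut of 1 − 2/3 = 33%. Level −2 is 1 mcg/kg, a cut of 1 − 1/3 = 67%. Against 2.25 and 1.5 these are 1 − 2/2.25 = 11% and 1 − 1/1.5 = 33% lower. They exceed what 2.2 asks for on base 3.

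**The case against.** The best defence is that the plan is less rigid than the gap suggests. The entry floor excludes known moderate impairment. Creatinine and weight are scheduled, so a fall would be seen. The 27 weeks of injections are qualified by tolerance, 3.5 and 4.4 allow the investigator to stop, no sentence forbids a reduction, and 2.2 itself tells investigators that one is recommended. A transplant patient in rejection would plausibly be stopped under 4.4.

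Much of this stands. A reader might infer that such a patient must stay at 3 mcg/kg for the rest of the 27 weeks; the documents do not support that, because stopping and the tolerance wording remain open. A reader might also infer a 33% or 100% overdose as fact. That holds only on base 3, and on base 6 there is no excess.

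What does not stand is that these provisions replace a dose rule. Stopping is not reducing. Tolerance wording acts once a patient is unwell, whereas a renal adjustment is meant to act on the laboratory value. The one sentence in 4.3 on reductions names severe side effects only. Nor does 5.1 fill the gap, since its reductions apply to the other drug. Rules keyed to a measurement are not foreign to this protocol: 5.1 holds treatment on Day 1 neutrophil and platelet counts, and 5.2 acts on weight loss above 10%, neither requiring a grade or an attribution.

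**Conclusion.** The point holds as a minor safety gap. For an on-treatment fall in clearance below 50 mL/min that is under grade 3, or is not attributed to interferon, the plan directs no interferon reduction, although Section 2.2 recommends one. What is missing is a dose rule, not data.

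Confidence is high that the rule is absent and much lower about harm. The size rests on two things the documents do not settle: the base for the percentages (2.25 and 1.5 mcg/kg if it is the 3 mcg/kg start) and the number of patients affected, which is unknown and probably small. The below-grade-3 part also depends on CTCAE cut-offs that are not in the documents. A reader might go on to infer damage to the response endpoint; nothing in the documents supports that, and none is claimed.

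**What to change.** 1. **Calculate clearance.** On Day 1 of each cycle, compute Cockcroft-Gault clearance from that day's creatinine and weight. The calendar shows cycles 1 to 3 only, so state that the tests and the calculation continue through cycle 9. For a patient enrolled on a 24-hour urine value, record a Cockcroft-Gault baseline and require a decline from it. Otherwise the change of method alone could trigger a cut with no real loss of function.

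2. **Add a renal rule to 5.2.** A value below 50 or below 29 mL/min, confirmed on repeat chemistry, reduces interferon by 25% or 50% (to 2.25 or 1.5 mcg/kg) whatever the grade or attribution. If the sponsor prefers existing levels, use Table 2 level −1 or −2 and accept the larger cuts of 33% and 67%. A patient already at a lower dose stays there. State whether the dose may be restored if clearance recovers.

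**Cost.** One paragraph in 5.2, one calendar line and one calculation per cycle, with no new routine test if the chemistry and weight shown for cycles 1 to 3 continue. The downside is a few more dose modifications, an occasional repeat chemistry, and somewhat lower interferon exposure in the patients concerned.

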### **3. PATIENT SELECTION**

#### **3.1 Inclusion Criteria**

- 3.1.1 Patients must have histologically or cytologically confirmed squamous cell carcinoma of the skin. Patients who present with "squamous cell carcinoma of unknown primary lesions" at the time of diagnosis will be eligible if patients have a plausible primary skin site removed in the past. Similarly, patients with neck, parotid, or facial lymph nodes positive for squamous cell carcinoma with no identifiable mucosal primary would also be eligible.

- 3.1.2 Patients must have measurable disease, defined by RECIST v1.1 as at least one lesion that can be accurately measured in at least one dimension of  $\geq 10$  mm by CT, MRI, or calipers. See section 9.2 for the evaluation of measurable disease.
- 3.1.3 There is no limitation to prior treatments with local, regional, topical or systemic agents, except for prior systemic treatment with 5-fluorouracil or prodrugs thereof. Prior topical treatment with 5-fluorouracil is permitted. Patients who are on chronic daily doses of prednisone of greater than 10 mg are excluded. There is no restriction on timing of last treatments as long as patients have recovered from all expected toxicities and at least 21 days have passed since last administration.
- 3.1.4 Age  $\geq 18$  years. Because no dosing or adverse event data are currently available on the use of 5-FU/Capecitabine or IFN alpha-2b in patients  $<18$  years of age, children are excluded from this study.
- 3.1.5 Life expectancy of greater than 3 months.
- 3.1.6 ECOG performance status  $\leq 2$  (Karnofsky  $\geq 60\%$ ; see Appendix A).
- 3.1.7 Patients must have normal organ and marrow function as defined below:
 

Absolute neutrophil count	$\geq 1,500/\text{mcL}$
Platelets	$\geq 75,000/\text{mcL}$
Total Bilirubin	$< \text{ULN}$ or up to 2x ULN if patient has clinically documented Gilbert's syndrome (elevated unconjugated bilirubin from decreased UGT1A1 activity)
AST(SGOT)/ALT(SGPT)	$\leq 2.5x$ institutional upper limit of normal or up to 5x ULN if known to be caused by liver metastasis
Creatinine Clearance	$\geq 50 \text{ mL/min}$ by either Cockcroft-Gault formula or 24 hr urine collection analysis.

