### 3.2 Exclusion Criteria

3.2.1 Patients who have had chemotherapy or radiotherapy within 21 days (6 weeks for nitrosoureas or mitomycin C) prior to entering the study or those who have not recovered from adverse events due to agents administered more than 3 weeks earlier.

3.2.2 Patients may not be receiving any other investigational agents.

3.2.3 Patients with known brain metastases should be excluded from this clinical trial because of their poor prognosis and because they often develop progressive neurologic dysfunction that would confound the evaluation of neurologic and other adverse events.

3.2.4 History of allergic reactions attributed to compounds of similar chemical or biologic composition to either 5-FU/Capecitabine or Interferon.

3.2.5 Uncontrolled, ongoing illness including, but not limited to, ongoing or active infection, symptomatic congestive heart failure, unstable angina pectoris, myocardial infarction <30 days, CVA/TIA <30 days, cardiac arrhythmia, or psychiatric illness/social situations that would limit compliance with study requirements.

3.2.6 Pregnant women are excluded from this study because 5-FU/Capecitabine is an anti-metabolite agent with the potential for teratogenic or abortifacient effects. Because there is an unknown but potential risk for adverse events in nursing infants secondary to treatment of the mother with 5-FU/Capecitabine, breastfeeding should be discontinued if the mother is treated with 5-FU/Capecitabine. Pregnancy testing will be completed on all female participants of child-bearing potential by urine analysis.

3.2.8 Any heart or lung transplant patient on immunosuppressive agents. Renal transplant patients are allowed if patient is willing to reduce immunosuppressive agents and understand risk of rejection and possible need to return to dialysis. Patients with CLL or other hematologic malignancies are allowed as long as they meet other criteria listed above.

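### The protocol contraindicates PEG-interferon in autoimmune hepatitis, but no visible eligibility criterion keeps out a patient with known, controlled disease

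*Combined protocol and SAP*

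**What the plan says.** Section 2.2 (PEG Interferon alpha-2b) lists three contraindications: "The drug is contraindicated for patients with a known hypersensitivity to IFN, patients with autoimmune hepatitis, or hepatic decompensation". The same section warns: "Severe adverse reactions include: neuropsychiatric reactions, arrhythmia, cardiovascular decompensation, retinopathy resulting in blindness, hepatic failure".

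The eligibility criteria that bear on these are:

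- **3.1.3 (steroids):** "Patients who are on chronic daily doses of prednisone of greater than 10 mg are excluded".
- **3.1.7 (organ function):** total bilirubin below ULN, or up to 2 times ULN with documented Gilbert's syndrome. AST/ALT may be up to 2.5 times the "institutional upper limit of normal or up to 5x ULN if known to be caused by liver metastasis".
- **3.2.4 (allergy):** "History of allergic reactions attributed to compounds of similar chemical or biologic composition to either 5-FU/Capecitabine or Interferon".
- **3.2.5 (concurrent illness):** opens with "Uncontrolled, ongoing illness including, but not limited to, ongoing or active infection" and goes on to cardiac, cerebrovascular and psychiatric examples.
- **3.2.8 (transplant):** "Any heart or lung transplant patient on immunosuppressive agents". Renal recipients may enter if they agree to reduce immunosuppression, and patients with hematologic malignancies may enter if they meet the other criteria.

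Section 4.3 starts interferon at 3 mcg/kg, given "every week for a total of 27 weeks as tolerated". The exclusion list goes from 3.2.6 straight to 3.2.8.

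**The concern.** Eligibility criteria are what a site applies, line by line, when it enrols a patient. A contraindication that appears only in the background section does not bind that decision. Hypersensitivity was turned into an exclusion, and decompensation is mostly caught by laboratory limits and the uncontrolled-illness rule. Autoimmune hepatitis, the remaining one of the three, has no counterpart.

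Section 2.2 does not limit this contraindication to active or severe disease, so controlled disease falls within it. At stake is patient safety: someone in whom the protocol itself contraindicates the drug could satisfy every written criterion and be treated, with hepatic failure on the protocol's own list of severe reactions.

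The scenario is not far-fetched for this trial. Section 2.1 links the rise in cutaneous squamous cell carcinoma partly to immunosuppressive agents, and 3.1.3 and 3.2.8 show that patients on low-dose steroids and renal transplant recipients are expected.

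**Working it through.** No sample-size or error-rate calculation applies. The check sets the Section 2.2 contraindications against the criteria.

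**Count of visible criteria.** Inclusion 3.1.1 to 3.1.10 gives 10. Exclusion 3.2.1 to 3.2.6 plus 3.2.8 gives 7. 10 + 7 = 17, of which 0 name autoimmune hepatitis.

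**Where each contraindication goes.**

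| Contraindication in 2.2 | Matching criterion |
|---|---|
| Interferon hypersensitivity | 3.2.4, directly |
| Hepatic decompensation | 3.1.7 and 3.2.5, largely |
| Autoimmune hepatitis | None visible for controlled disease |

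**Test case.** Take a patient with known autoimmune hepatitis, controlled on prednisone 10 mg/day or less, bilirubin below ULN and AST/ALT at or below 2.5 times ULN, who is otherwise eligible.

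| Provision | Result for this patient |
|---|---|
| 3.1.3 | Not excluded: it stops only chronic prednisone above 10 mg/day |
| 3.1.7 | Met: it tests laboratory values, not diagnoses. The 5 times ULN allowance, which is for liver metastasis only, is not needed |
| 3.1.8 | Tumor board review is required, but its stated purpose is to verify unresectability |
| 3.2.4 | Not applicable: no allergy |
| 3.2.5 | Not applicable: the list of illnesses is open-ended, but the illness must still be uncontrolled |
| 3.2.8 | Not applicable: not a transplant patient |
| 3.5 | Removal for failing eligibility does not apply, because the patient meets the criteria |

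On the visible text, the patient is eligible.

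**After entry.** The ceiling on exposure is 9 cycles × 3 weekly doses = 27 doses, which agrees with the 27 weeks in Section 4.3. The Section 8 calendar shows serum chemistry in weeks 1, 4 and 7, so the doses of weeks 1, 2 and 3 (3 doses) come before the week 4 test. These counts describe the schedule for any patient; they do not measure harm. Section 5.2 acts on grade 3 or 4 toxicity and allows a restart once it has resolved to grade 1 or better. Its symptom-specific rules cover fatigue, arthralgia and myalgia, weight loss, depression and gastrointestinal toxicity; none is hepatic.

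**The case against.** There are four points on the other side.

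1. **A criterion may be missing from view.** The numbering skips 3.2.7, and a lost item would not be an error in the plan. This stands as a caveat. Nothing marks a removal there, so a skipped number is equally possible, and the sponsor has to say which it is.
2. **The protocol already carries the warning.** Section 2.2 is part of the protocol, medical history is taken before the study, and treatment is given at a single centre. A careful investigator would probably act on this. It remains true that no visible criterion requires the patient to be excluded.
3. **The remaining group is very narrow.** Prednisone above 10 mg/day, abnormal liver tests and uncontrolled disease are all screened out, and planned enrolment is only 30 patients. The documents do not show that even one such patient is to be expected. This bears on how much weight the point carries, not on whether the gap exists.
4. **There are safeguards on treatment.** Chemistry is checked each cycle, and laboratory tests are repeated within 48 hours before the next cycle if the patient is deteriorating. Section 5.2 withholds treatment for up to 3 weeks and withdraws the patient if the toxicity does not resolve. Section 4.4 lets the investigator stop, and the Data and Safety Monitoring Committee reviews serious adverse events. All of these act after exposure, so they limit harm without preventing entry.

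**Conclusion.** The concern holds on the visible text. One of the three contraindications stated in Section 2.2 has no matching criterion for its known, controlled form, and the criteria as written would admit such a patient. The consequence is confined to safety and eligibility: the endpoint, the analysis and the two-stage design with its error rates are untouched. The number of patients affected is probably very small and cannot be estimated from the documents.

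The conclusion assumes that no 3.2.7 covering autoimmune hepatitis exists, and it reads the contraindication as Section 2.2 words it, without restriction to active disease. Confidence is medium, mainly because of the gap in the numbering. The change should be made, since it brings the criteria into line with the protocol's own safety statement at almost no cost.

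**What to change.** First confirm whether a criterion 3.2.7 exists and covers this. If it does not, add one exclusion to Section 3.2: *Known history of autoimmune hepatitis*, to be identified from the pre-study medical history already on the Section 8 calendar. Naming hepatic decompensation in the same line is optional; it would align the list with Section 2.2, although 3.1.7 and 3.2.5 already largely screen for it.

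The cost is one line of text. The loss of eligible patients should be negligible, no test or visit is added, and the two-stage design of 16 and then 25 evaluable patients stays as it is.
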